# **10.3 Populations for analyses**

# 10.3.1 Safety set

The safety set includes all patients who received at least one dose of bimiralisib.

# 10.3.2 Per-protocol set

The per-protocol set (PPS) consists of a subset of the safety set who are compliant with requirements of the clinical study protocol. All protocol deviations or conditions leading to exclusion from the PPS will be detailed in the data handling plan and statistical analysis plan.

#### 10.3.3 Pharmacokinetic analysis set

The PK analysis set (PAS) will consist of all patients who receive at least one dose of bimiralisib and have at least one evaluable concentration measurement. PK data will be reported separately.

# **10.4** Statistical analyses

Detailed data handling methods will be addressed in the statistical analysis plan.

# **10.4.1** Efficacy analyses

All efficacy analyses will be performed on the PPS.

ORR including confirmed complete response (CR), and confirmed partial response (PR) is the primary endpoint.

Frequency and percentage of the ORR with a two-sided 95%-confidence interval will be determined.

Secondary endpoints include additional clinical efficacy assessment by time to response (TTR), duration of response (DOR), time to treatment failure (TTF) and progression-free survival (PFS).

Time to event data will be summarized using the Kaplan-Meier methodology.

Time to response (TTR) is defined as the time from first study drug administration to the first documentation of response (complete or partial).

Duration of response (DOR) is defined as the time from the date of the first confirmed response to the first documentation of disease progression, whichever occurs first

Progression- free survival (PFS) is defined as the time from first study drug administration to disease progression or death due to any cause.

Time to treatment failure (TTF) is defined as the time from first study drug administration to any treatment failure including disease progression or discontinuation of treatment for any reason (e.g., disease progression, AE, patient withdrawal of consent, initiation of new treatment without documented progression, death)

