## Table 4: Treatment interruptions and dose reductions for adverse events (except hyperglycaemia) considered related to bimiralisib by the treating physician

Reason	Treatment change
Non-haematological AE Grade 4	Stop bimiralisib treatment permanently.
Haematological AE Grade 4	Interrupt bimiralisib treatment. If AE resolves to baseline or CTCAE grade 1 within 7 days, patients may resume treatment at the reduced dose of 100mg. If AE resolves within 8 to 14 days, patient may resume treatment at the reduced dose of 100mg if agreed between investigator and sponsor. If AE does not resolve to baseline or CTCAE grade 1 within 14 days, bimiralisib treatment must be discontinued permanently.
Grade 3 AE	Interrupt bimiralisib treatment. If AE resolves to baseline or CTCAE grade 1 within 7 days, patient may resume treatment at 140mg. If AE resolves to CTCAE grade 1 within 8 to 14 days, patient may resume treatment at the reduced dose of 100mg. If AE does not resolve to baseline or CTCAE grade 1 within 14 days, bimiralisib treatment must be discontinued permanently.
Any non-haematological AE grade 2	Continue bimiralisib treatment. Dose reduction at the discretion of the treating physician

Patients who after dose interruption do not tolerate bimiralisib treatment at 100 mg must be permanently discontinued. If during the first three months on study, a patient cannot restart at the 100 mg dose level within 14 days, this patient is not evaluable for the primary endpoint, and the investigator must discuss the individual benefit-risk evaluation of this patient with the sponsor before restarting dosing. These patients may be replaced.

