# 9.11 Patient Replacement

If patients withdraw consent or drop out for other reasons unrelated to safety or disease progression, they may be replaced. This includes patients who start smoking (as evidenced by cotinine test) within the first 12 weeks on bimiralisib treatment. These patients may remain on treatment but will be replaced. Patients who start smoking after the first 12 weeks on bimiralisib treatment will not be replaced. Patients for whom IHC analyses indicate high protein levels of NICD which are deemed incompatible with NOTCH1 loss-of-function may be replaced.

In total, we anticipate up to 20% of patients to drop out, resulting in enrollment of up to 35 patients in total.

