# 10.4.2 Safety analyses

### **10.4.2.1** Analysis set and grouping for the analyses

For primary safety analyses, the safety set will be used.

The assessment of safety will be based mainly on the frequency of adverse events and on the number of laboratory values that fall outside of pre-determined ranges. Other safety data (e.g., ECG, vital signs) will be considered as appropriate. All safety data will be listed.

The overall observation period will be divided into three mutually exclusive segments:

1. Pre-treatment period: from day of ICF signature to the day before first dose of bimiralisib

- 2. On-treatment period: from day of first dose of bimiralisib to 30 days after last dose of bimiralisib
- 3. Post-treatment period: starting at day 31 after last dose of bimiralisib

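### The primary ORR is analysed only in the per-protocol set, which drops early toxicity failures, and the supplied documents plan no ORR in all treated patients

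*Protocol*

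**What the plan says.** - **Analysis set.** Protocol Section 10.4.1: "All efficacy analyses will be performed on the PPS". Section 10.3.2 defines the PPS as the protocol-compliant part of the safety set and leaves the exclusion rules to a data handling plan and the SAP.
- **All-treated set.** Section 10.3.1: "The safety set includes all patients who received at least one dose of bimiralisib". Its only stated use is in Section 10.4.2.1: "For primary safety analyses, the safety set will be used".
- **Toxicity exit.** Section 7.2, in the text below the dose-reduction table: "If during the first three months on study, a patient cannot restart at the 100 mg dose level within 14 days", then "this patient is not evaluable for the primary endpoint". The same paragraph says that these patients may be replaced.
- **Other exits.** Section 9.11 covers withdrawal and other dropout: "If patients withdraw consent or drop out for other reasons unrelated to safety or disease progression, they may be replaced". For patients who start smoking in the first 12 weeks it says: "These patients may remain on treatment but will be replaced". On archival staining it says: "Patients for whom IHC analyses indicate high protein levels of NICD which are deemed incompatible with NOTCH1 loss-of-function may be replaced". General non-compliance is a further way out of the PPS (Section 10.3.2).
- **Decision rule.** Section 10.2 and SAP Section 1.2 give 10 patients in stage 1, continuation with two or more responses, 19 more in stage 2, and rejection of an ORR of 10% or less with six or more responses in 29. Up to 35 may be enrolled.
- **Timing.** Section 9.3 requires at least two on-treatment assessments to confirm a response and schedules the first two for Days 43 and 85, each with a window of 3 days either way.

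**The concern.** A patient who takes the drug and cannot continue because of toxicity belongs to the population the trial is about. Counting that patient as a non-responder would be the ordinary treatment in an ORR. Section 7.2 instead removes the patient from the primary endpoint and allows another to take the place. Both scheduled scans needed for confirmation fall within or close to the end of the three-month window, so most patients removed this way will have had no chance to show a confirmed response. The denominator then loses mainly non-responders and the ORR tends to rise.

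The other exits matter less. Early smoking and high NICD have a rationale tied to the target population, although the supplied text gives no NICD cut-off. Withdrawal and other dropout are common in such trials, but they too reduce the set to patients who stayed.

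The stake is how the result is read. An ORR reported only in patients who tolerated the drug and complied is not the ORR a new patient starting treatment can expect. The supplied plan gives no second figure showing the difference.

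**Working it through.** **1. Reproduce the design.** Inputs from Protocol Section 10.2 and SAP Section 1.2: n1 = 10, continue if at least 2 respond, n2 = 19, reject if at least 6 respond in total, p0 = 0.10, p1 = 0.30.

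P(reject | p) = sum over x = 2 to 10 of P(Bin(10, p) = x) × P(Bin(19, p) ≥ 6 − x).

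At p = 0.10:

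| Stage 1 responses | Probability | Chance of reaching 6 | Product |
|---|---|---|---|
| 2 | 0.1937 | 0.1150 | 0.0223 |
| 3 | 0.0574 | 0.2946 | 0.0169 |
| 4 | 0.0112 | 0.5797 | 0.0065 |
| 5 | 0.0015 | 0.8649 | 0.0013 |
| 6 or more | 0.0001 | 1 | 0.0001 |

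The sum is 0.0471. The same formula at p = 0.30 gives 0.8051. The stated 5% one-sided level and 80% power are reproduced. They hold when the 29 analysed patients represent the treated population with respect to response.

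**2. Effect on the estimate.** Take the smallest positive result, 6 responders in a PPS of 29, and suppose k further treated patients left under Section 7.2 without a response and were replaced. The all-treated ORR is 6/(29 + k), with Clopper-Pearson 95% limits:

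| k | ORR | 95% CI |
|---|---|---|
| 0 (PPS figure) | 6/29 = 20.7% | 8.0 to 39.7 |
| 1 | 6/30 = 20.0% | 7.7 to 38.6 |
| 2 | 6/31 = 19.4% | 7.5 to 37.5 |
| 3 | 6/32 = 18.8% | 7.2 to 36.4 |

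**3. Effect on the error rate if removed patients are replaced.** The documents give no rate for the Section 7.2 exit, so a share f of 5% to 10% of treated patients is assumed, none of them responding and all replaced. The PPS response probability is then 0.10/(1 − f) when the true all-treated ORR is 10%.

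- f = 0.05: 0.10/0.95 = 0.1053, P(reject) = 0.058.
- f = 0.10: 0.10/0.90 = 0.1111, P(reject) = 0.071.
- If the removed patients respond like the rest, P(reject) stays at 0.047.

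**4. Effect if they are not replaced.** Keep the cut-off of 6 and shorten stage 2, with p = 0.10 and p = 0.30 in the same formula:

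- 10 + 17: P(reject) = 0.037, power 0.779.
- 10 + 15: P(reject) = 0.028, power 0.740.

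Step 3 raises the rejection probability above the design level and step 4 lowers it. Which applies depends on a replacement rule that the protocol states in two ways. Section 7.2 allows replacement after toxicity. Sections 4.1, 9.11 and 10.2 describe replacement for dropout unrelated to safety. Neither side refers to the other.

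**The case against.** Several points on the other side are sound.

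- **Rules may exist elsewhere.** The data handling plan was not supplied, and the supplied SAP covers only hypotheses and sample size. PPS criteria, or even an all-treated ORR, could be set out there. This limits the claim to the supplied text. It does not remove the claim, because Section 10.4.1 assigns every efficacy analysis to the PPS.
- **The shift is modest.** A change from 20.7% to 18.8% is small beside an interval from 8.0 to 39.7. This stands.
- **A reader could get part of the way.** If the final report gives the size of the safety set, PPS responders divided by treated patients is a lower bound, for example 6/35 = 17.1% at the enrolment ceiling, if all 35 were treated. Responses among removed patients would still be missing.
- **The null hypothesis is not explicitly all-treated.** The 0.058 to 0.071 figures measure the rule against an all-treated ORR of 10%, a population the protocol does not name for its hypothesis.

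A reader might go further and infer that the plan lets non-responders be swapped out once their scans are known, since the trial is open label and Section 12.1.8 has the principal investigator and sponsor review tumor response at least every 2 months. The documents do not support that. No text directs removal on the basis of response, Section 9.11 does not offer replacement for progression, and the Section 7.2 rule would remove a responder as well. For illustration only, one non-responder selectively replaced would give a rejection probability of 0.053 in stage 2 or 0.057 in stage 1.

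**Conclusion.** The concern holds for the estimate. On the supplied text, the primary ORR excludes treated patients who fail early on toxicity, those patients will usually lack a confirmed response, and no ORR in all treated patients is planned. The reported ORR therefore tends to be biased upward, by about 2 percentage points at the smallest positive result if three such patients are replaced (20.7% against 18.8%). This rests on their having no confirmed response, which is likely but not certain.

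It might be inferred that the type I error is inflated. That does not follow from the documents. It rises to 0.058 to 0.071 only if 5% to 10% of treated patients (an assumed range) leave this way, none responds and all are replaced. It falls to 0.037 or 0.028 if two or four patients are lost from stage 2 without replacement and the cut-off stays at 6. It is unchanged if removal is unrelated to response and patients are replaced. Smoking and NICD replacement alone would not alter the error level for the intended population if off-target patients simply respond less.

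This should be fixed. Confidence is high that the supplied text lacks an all-treated ORR, and moderate on the PPS rules and the direction of the error rate.

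**What to change.** 1. **Add a supportive all-treated ORR.** Pre-specify the ORR with 95% CI in the safety set, counting anyone without a confirmed response as a non-responder. Beside it, apply the 2-of-10 and 6-of-29 rules to the first 10 and first 29 treated patients in enrolment order. For that version the rejection probability at an all-treated ORR of 10% or less is at most 0.0471, whatever the replacement process. The same set can serve PFS and TTF.
2. **Write the PPS exclusion rules down before the response data are analysed.** List every removed or replaced patient with the reason, the date and the response status at that time. Replacement decisions blind to response are not requested. In an open-label trial whose investigator and sponsor review response, they would need a separate decision-maker.
3. **Reconcile Section 7.2 with Sections 4.1, 9.11 and 10.2** on whether patients may be replaced after toxicity.

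The cost is protocol and SAP wording, a few tables and one listing, with no extra patients or visits. A slightly lower ORR will stand beside the PPS figure. Power is unchanged while the analysis stays supportive. If the sponsor made the all-treated rule the primary decision, power at a true 30% would fall from 0.805 to 0.766 with 5% of would-be responders lost (0.30 × 0.95 = 0.285) and to 0.720 with 10% lost (0.30 × 0.90 = 0.27).

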# 9.3 Efficacy assessments

Radiological tumor assessments will be performed by CT or MRI according to a standard protocol at baseline (BL), every 6 weeks ( $\pm$  3 days) until disease progression, starting of another anti-neoplastic treatment, or death whichever occurs first.

Response evaluation criteria in solid tumors (RECIST), version 1.1, will serve to evaluate responses to bimiralisib treatment.

For the futility analysis, only a confirmed partial response (PR) or confirmed complete response (CR) are considered a response to treatment.

Confirmation of a treatment response requires at least two on-treatment response assessments. As per protocol, the first two on-treatment response assessments are scheduled for day 43 (+/-3 days) and day 85 (+/-3 days), respectively. If a treatment response in a patient does not meet the RECIST criteria for a partial response at the first response assessment, confirmation of a potential response might occur only at subsequent later on-treatment response assessments

PET scans are not permitted for efficacy assessment. If a patient has undergone radiological tumor assessment prior to consenting to the study, the data may be used as the baseline assessment if the imaging protocol is in line with the standard imaging protocol of the study and if the assessment was performed within 28 days of receiving the first dose of bimiralisib.

All reasonable effort should be made for radiological imaging used for tumor assessments to be read by one dedicated local radiologist at each study center. Results must be reported in the CRF. ORR, TTR, DOR, TTF and PFS will be determined according to the response evaluation criteria in solid tumors (RECIST), version 1.1 [2].

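### Time to response falls under Kaplan-Meier with no rule for patients who progress or die without responding; if they are censored, the curve can overstate the probability of response

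*Protocol*

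**What the plan says.** Protocol section 10.4.1 contains three statements that together govern TTR:

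- The analysis set: "All efficacy analyses will be performed on the PPS".
- The method: "Time to event data will be summarized using the Kaplan-Meier methodology".
- The endpoint: "Time to response (TTR) is defined as the time from first study drug administration to the first documentation of response (complete or partial" (the bracket closes there in the source). TTR stands beside DOR, TTF and PFS in the list of secondary endpoints.

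The primary endpoint is handled differently: "Frequency and percentage of the ORR with a two-sided 95%-confidence interval will be determined". It counts only confirmed complete and partial responses.

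Protocol section 9.3 sets the follow-up for response. Scans run "until disease progression, starting of another anti-neoplastic treatment, or death whichever occurs first", and "the first two on-treatment response assessments are scheduled for day 43 (+/-3 days) and day 85 (+/-3 days), respectively". The table of assessments continues them at week 18 and every 6 weeks after that.

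On censoring, Protocol section 10.4 says only that "Detailed data handling methods will be addressed in the statistical analysis plan". The SAP text available for this review has sections 1.1 (hypotheses) and 1.2 (sample size) and holds no rule for TTR or for censoring.

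**The concern.** TTR starts at first dose, so every PPS patient has a start time and, on a plain reading, enters the risk set. A patient who progresses or dies without responding can no longer have a response counted. Kaplan-Meier has no state for such a patient. If the patient is censored, the estimator assumes a later response at the same rate as in those still under observation. One minus Kaplan-Meier then estimates response in a setting where nobody progresses or dies, which is not the quantity the trial reports as ORR.

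The practical risk is two response probabilities in one report: the ORR as a simple proportion, and a TTR curve that ends higher. A reader could take the curve for the response rate.

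A second, smaller issue is that the TTR definition does not say confirmed. As written, a partial response seen at day 43 and not confirmed later could count as a TTR event but not as an ORR event.

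**Working it through.** **The plan's own figures.** The documents give no figure for TTR. The related figure is the Simon design: stop if 1 or fewer of 10 respond, reject H0 if 6 or more of 29 respond. The probability of rejection is the sum over x = 2 to 10 of P(X1 = x) × P(X2 ≥ 6 − x), with X1 binomial on 10 patients and X2 on 19. This gives 0.0471 at a response rate of 10% and 0.805 at 30%, so the stated one-sided 0.05 and 80% power reproduce. Six of 29 (20.7%) is the smallest count that rejects H0, and it serves as the worked case.

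**Inputs for TTR.**
- From the documents: 29 patients; scans at days 43 and 85, then every 6 weeks (days 127 and 169).
- Assumed: all 29 patients are in the PPS, and the 23 non-responders leave at days 43, 85, 127 and 169 in numbers 12, 6, 3 and 2. Response timing is varied.

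**Formula.** S = product over scans of (1 − responses / number at risk). The number at risk falls by both responders and non-responders who left at earlier scans. The estimated probability of response is 1 − S.

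| First response at day 43 / 85 / 127 / 169 | S | 1 − S | Observed |
|---|---|---|---|
| 6 / 0 / 0 / 0 | 23/29 | 20.7% | 20.7% |
| 4 / 2 / 0 / 0 | 25/29 × 11/13 | 27.1% | 20.7% |
| 3 / 2 / 1 / 0 | 26/29 × 12/14 × 5/6 | 36.0% | 20.7% |
| 3 / 1 / 1 / 1 | 26/29 × 13/14 × 6/7 × 2/3 | 52.4% | 20.7% |

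In the third row, for example, the number at risk at day 85 is 29 − 3 − 12 = 14, and at day 127 it is 14 − 2 − 6 = 6.

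**Cumulative incidence on the same data.** Each response is weighted by the probability of still being free of response, progression and death. For the third row this is 3/29 + (14/29)(2/14) + (6/29)(1/6) = 6/29 = 20.7%, which equals the observed proportion. Kaplan-Meier with non-responders kept at risk to the end of follow-up also gives 20.7%.

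**Average over repeated trials.** Simulated trials of 29 patients, 3,000 per setting, with a true ORR of 30%. The progression hazard in non-responders is 0.307 per 6-week interval, from 1 − 0.23^(1/4). The 23% is a 6-month PFS that Protocol section 2.1 cites for a different drug, so it is an illustration only.

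| Share of responses first seen at scans 1 / 2 / 3 / 4 | Mean of 1 − S |
|---|---|
| 100 / 0 / 0 / 0 | 30.1% |
| 70 / 30 / 0 / 0 | 33.4% |
| 50 / 30 / 20 / 0 | 38.0% |
| 40 / 30 / 20 / 10 | 42.5% |

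Over hazards of 0.20 to 0.50, and with some responses after the first scan, the mean runs from 32.0% to 57.6% at a true ORR of 30%, and from 10.6% to 23.8% at a true ORR of 10%.

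**The case against.** The strongest reply is that the plan nowhere says progression is censored. That is correct. A reader might infer a written censoring rule from the Kaplan-Meier sentence, but there is none: section 10.4 leaves data handling to the SAP, and the available SAP text is silent. A rule keeping non-responders at risk to the end of follow-up would remove the bias. What stands is that no rule prevents the ordinary default. With scans ending at progression, new treatment or death, that default censors at about that point.

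It can also be said that the PPS sentence covers DOR, which exists only in responders, so the sentence cannot exclude a responder subset for TTR. The synopsis adds that other efficacy endpoints are summarised descriptively. This is a fair reading, and a responder-only Kaplan-Meier would have no censoring. But the DOR clock starts at response, which restricts it by definition, while the TTR clock starts at first dose. The four additional efficacy endpoints in the synopsis are all times to an event, so the plainer reading puts TTR under Kaplan-Meier.

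A reader might also infer that the curve must end above the ORR. It need not: the excess is zero if all responses come at the first scan and nobody leaves before it. Section 9.3 does allow for a response that first meets the criteria at a later scan, so an excess is possible but not certain.

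Nor will a misleading median usually be printed. While 1 − S stays below 50%, the median is simply not reached. Among the four worked patterns it is reached only in the last, at day 169.

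On confirmation, the first documentation of response may well mean the first scan of a response later confirmed. The text does not settle this, so it is an ambiguity and not a proven mismatch.

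**Conclusion.** The point holds in conditional form. Section 10.4.1 applies Kaplan-Meier to TTR on the PPS, with no restriction to responders and no rule for patients who progress or die without responding. If they are censored when scans stop, the curve overstates the probability of response whenever some responses follow earlier exits. In the worked case of 6 responders in 29, the excess over 20.7% runs from nothing to 15.3 percentage points (36.0 − 20.7) across the first three patterns, and to 31.7 points (52.4 − 20.7) in the most spread-out one. All of these rest on assumed response and exit times. The documents give neither, nor any rate of unconfirmed response, so the effect of the confirmation ambiguity is not quantified.

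A reader might take this as a threat to the trial's conclusion. The documents do not support that: ORR, the stage 1 rule and the test of H0 all use simple counts of confirmed responses, and no decision uses the TTR curve. It is a minor point about a secondary endpoint, worth correcting because the correction is cheap.

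**What to change.** In Protocol section 10.4.1 and the SAP, exclude TTR from the Kaplan-Meier sentence and state instead:

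- TTR is summarised as median and range among patients with a confirmed response.
- It runs from first dose to the first scan of the response that was later confirmed.
- If a curve is wanted, it is the cumulative incidence of confirmed response in the whole analysis set, with progression and death as competing events.

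Kaplan-Meier can remain for PFS, TTF and DOR. The DOR definition names only progression as its end, so the same edit should say how death is handled there.

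The cost is about one sentence in each document and no extra data. The downside is that the responder-only summary is conditional on response. It describes how soon responses appear, not how likely they are, and should be shown next to the ORR.

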### **3** Study purpose, objectives and endpoints

The main purpose of this study is to determine the objective response rate (ORR) of patients with r/m HNSCC harboring *NOTCH1* LOF mutations to oral bimiralisib. The ORR comprises patients with confirmed partial response (PR) or confirmed complete response (CR) as per RECIST version 1.1 [2, 3].

The study objectives and related endpoints are summarized in Table 3.

Protocol PQR309-009

PIQUR Therapeutics AG - Confidential

Version 5.0

Amendment date: see date of last approval

Table 3:Objectives and related endpoints

I able 3: Objectives and related enapoints		
Objective(s)	Endpoint(s)	Assessment Description
Primary		
To determine the objective response rate (ORR) of patients with r/m HNSCC harboring NOTCH1 LOF mutations to oral bimiralisib	ORR: comprised of all patients who achieved a confirmed partial or a confirmed complete response	Section 9.3
Secondary		
To evaluate the safety of bimiralisib in patients with r/m HNSCC harboring NOTCH1 LOF mutations	
 
Overall SAEs
 
Overall SAEs
 
SAEs resulting in death
 
SAEs resulting in discontinuation
 
SAEs resulting in dose reduction or dose interruption
 
SAEs resulting in dose reduction or dose interruption
 
Changes from baseline in:
 
body weight,
 
vital signs,
 
ECOG performance status,
 
ECO,
 
hematology,
 
hematology,
 
biochemistry and
 
Patient Health Questionmaire (PHQ)-9 and General Anxiety Disorder (GAD)-7 mood scale score
 
	Section 9.4

Page 23 of 81

Protocol PQR309-009 PI	PIQUR Therapeutics AG - Confidential	Version 5.0
	Amendm	Amendment date: see date of last approval
Objective(s)	Endpoint(s)	Assessment Description
To evaluate additional clinical efficacy parameters of bimiralisib in patients with r/m HNSCC harboring NOTCH1 LOF mutations	TTR, DOR, TTF and PFS, evaluated according to RECIST version 1.1 [2, 3].	Section 9.3
To evaluate the pharmacokinetics of bimiralisib in patients with r/m HNSCC harboring NOTCH1 LOF mutations	Bimiralisib plasma concentrations. To be reported separately.	Section 9.6
Exploratory		
To determine if bimiralisib affects the size and number of pre-cancerous keratinocytic lesions (actinic keratosis)	Number and size of index lesions	Section 9.7.1

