# 10.4.2.2 Adverse events (AEs)

Summary tables for adverse events will include only adverse events that started or worsened during the on-treatment period, i.e. *treatment-emergent* adverse events.

The incidence of treatment-emergent adverse events (new or worsening from baseline) will be summarized by system organ class and/or preferred term, severity (based on CTCAE version 5.0 grades), type of adverse event, relation to study treatment by treatment arm. Deaths reportable as serious adverse events and non-fatal serious adverse events will be listed by patient and tabulated by type of adverse event and treatment arm.

Serious adverse events and non-serious adverse events during the on-treatment period will be tabulated.

All deaths (on-treatment and post-treatment) will be summarized.

All AEs, deaths and serious adverse events (including those from the pre and post-treatment periods) will be listed and those collected during the pre-treatment and post-treatment period will be flagged.

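### As defined, duration of response ends only at documented progression, so a responder who dies without it is censored although the same death is a PFS event; time to response also omits the confirmation that ORR requires

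*Protocol*

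**What the plan says.** All the definitions stand together in protocol section 10.4.1 (Efficacy analyses):

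- **DOR:** "time from the date of the first confirmed response to the first documentation of disease progression, whichever occurs first".
- **PFS:** "time from first study drug administration to disease progression or death due to any cause".
- **TTF:** any treatment failure, with a list of examples that ends "initiation of new treatment without documented progression, death".
- **ORR:** "ORR including confirmed complete response (CR), and confirmed partial response (PR) is the primary endpoint".
- **TTR:** "time from first study drug administration to the first documentation of response (complete or partial").

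The same section prescribes Kaplan-Meier summaries for time-to-event data and states no censoring rule. The synopsis, Table 3 and section 9.3 list TTR and DOR with a reference to RECIST 1.1 but add no event, censoring or confirmation rule; section 9.3, for example, says "ORR, TTR, DOR, TTF and PFS will be determined according to the response evaluation criteria in solid tumors (RECIST), version 1.1". Section 10.4 leaves data handling to the SAP. The SAP text available (sections 1.1 and 1.2) covers only hypotheses and sample size.

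**The concern.** The DOR sentence promises the earlier of two events and names one, so a second event appears to have been lost. If an analyst programs the sentence as it stands, a responder's death without documented progression is not an event. DOR and PFS would then treat the same death, on the same date, in opposite ways, and the DOR curve would sit higher than one that counts death. With only a handful of responders, one patient is enough to be visible.

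A smaller mismatch concerns TTR. ORR counts confirmed responses only, but TTR ends at the first documentation of a response and does not say that the response must later be confirmed. Read literally, a patient with an unconfirmed partial response has a TTR event without being an ORR responder, so TTR could describe a wider group than ORR and DOR.

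A third item is clarification only. The DOR start date could be the first scan showing a response that is later confirmed, or the confirming scan.

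**Working it through.** **1. The plan's own design figure.** The inputs from protocol section 10.2 are: stop at 0 or 1 responses in 10, add 19 patients, reject at 6 or more of 29, with ORR 10% against 30%. The exact two-stage binomial gives a one-sided type I error of 0.0471 and power of 0.8051, in line with the stated 0.05 and 80%. DOR and TTR do not enter this calculation, so nothing here changes.

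**2. Ending events side by side (section 10.4.1).**

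| Endpoint | Progression | Death |
|---|---|---|
| PFS | event | event |
| TTF | event | event |
| DOR | event | not named |

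Kaplan-Meier allows an event or a censoring. If death is not an event, a responder who dies without documented progression has to be censored. The documents do not state this; it follows from the event definition and the estimator.

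**3. Expected number of responders.**

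- With 29 patients: 29 × 0.10 = 2.9 and 29 × 0.30 = 8.7.
- Given that stage 2 opens: E[X1 | X1 ≥ 2] + 19p, where X1 is the number of responses in the first 10. This is 2.32 + 1.90 = 4.22 at 10% and 3.38 + 5.70 = 9.08 at 30%.

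**4. Effect of one such death.** With k responders at risk, counting the death multiplies the survival estimate by (k-1)/k, and censoring it omits that factor. Later estimates are therefore k/(k-1) times those with death counted, until the curve reaches zero: 3/2 = 1.50, 6/5 = 1.20 and 9/8 = 1.125 at k = 3, 6 and 9.

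**5. Six responders, the rejection threshold, with no other censoring.** Kaplan-Meier estimate after each ordered ending event:

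| Event | Death counted | Censored, death 1st | Censored, death 2nd | Censored, death 3rd |
|---|---|---|---|---|
| 1 | 0.833 | 1.000 | 0.833 | 0.833 |
| 2 | 0.667 | 0.800 | 0.833 | 0.667 |
| 3 | 0.500 | 0.600 | 0.625 | 0.667 |
| 4 | 0.333 | 0.400 | 0.417 | 0.444 |
| 5 | 0.167 | 0.200 | 0.208 | 0.222 |
| 6 | 0 | 0 | 0 | 0 |

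Taking the median as the first time the estimate is at or below 0.5, it falls at the 3rd event time with the death counted. It moves to the 4th when the death is censored, in all three cases. With assumed durations of 6, 12, 18, 24, 30 and 36 weeks and the 12-week one a death, the median is 18 weeks if the death counts and 24 weeks if it is censored.

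**6. DOR start date (clarification).** Section 9.3 schedules the first two scans for day 43 and day 85, each ±3 days. The two readings differ by 85 - 43 = 42 days, with a range from 82 - 46 = 36 to 88 - 40 = 48 days.

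**The case against.** The strongest reply has five parts.

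- **No censoring rule is written, and the missing event is not identified.** An analyst who sees an obviously incomplete sentence would probably query it, and TTF also lists new treatment and discontinuation. It is true that the documents never say which event was lost, and that censoring is an inference. But no other handling fits the named event and Kaplan-Meier, and death is the only second event that PFS names.
- **Progression-only duration is a legitimate estimand.** The upward shift is therefore relative to a DOR that includes death. That is correct. The closing phrase shows, however, that a single-event definition was not intended.
- **The SAP may settle the matter.** Only its hypotheses and sample-size sections are available, so missing censoring rules cannot be held against it. Even so, the protocol sentence needs correcting.
- **The size is hypothetical.** No rate of death without progression is given, and such a death must fall in a responder before documented progression and within follow-up. The median shift also depends on convention. With the death counted, the estimate is exactly 0.500 between the 3rd and 4th times; a midpoint rule would put the median halfway between them and halve the shift. This stands as a limit on the example. The k/(k-1) factors do not depend on it.
- **First documentation in TTR may be only a dating convention.** That is a fair reading, but the text does not limit TTR to confirmed responders, and a few words would do so.

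**Conclusion.** The concern holds. The DOR definition is wrong as written: it names one event where its own wording needs two, and it conflicts with the handling of death in PFS and TTF beside it. Nothing in the available documents repairs it.

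The expected bias cannot be derived. Conditional on one such death, later DOR estimates are higher by a factor of 1.125 to 1.50 for 9 down to 3 responders at risk. With six responders and no other censoring, the median can move by one event time. This assumes that death is the intended second event and that the definition is applied literally.

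The TTR mismatch is real but smaller, and the DOR start date is a clarification. DOR and TTR are descriptive secondary endpoints, so the primary ORR test, the futility rule, the power and the sample size are untouched. The wording should be corrected before analysis.

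**What to change.** Amend two sentences in protocol section 10.4.1 and match them in the SAP:

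- **DOR:** in the patients with confirmed CR or PR counted in ORR, end at first documented progression or death from any cause, whichever is earlier.
- **TTR:** restrict it to the same confirmed responders.
- **Clarification:** state that TTR ends, and DOR starts, at the first documentation of the response that is later confirmed.
- **Censoring:** state the rules in the SAP if its full text does not already do so. How to handle new anti-cancer therapy is for the sponsor to decide.

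No new assessments are needed. Scan dates are collected, and section 10.4.2.2 already provides that "All deaths (on-treatment and post-treatment) will be summarized". One limit remains: under section 9.5.1, investigators need not actively seek events after a patient's participation ends, so late deaths may be incompletely captured. The only other cost is that the reported DOR may be shorter.
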